## 8.2 Consent

The Principal Investigator (PI) retains overall responsibility for the informed consent of participants at their site and must ensure that any person delegated responsibility to participate in the informed consent process is duly authorised, trained and competent to participate according to the ethically approved protocol, principles of Good Clinical Practice (GCP) and Declaration of Helsinki. If delegation of consent is acceptable then details should be provided.

Informed consent must be obtained prior to the participant undergoing procedures that are specifically for the purposes of the trial and are out-with standard routine care at the participating site. Data can only be collected if informed consent form is signed at the screening visit. In daily practice, this is often not the case since patients want to overthink participation. Throughout the pilot study, several patients that were willing to participate but recovered before informed consent form was signed. This data is lost.

To tackle this issue, we will train and encourage centers to contact patients about the study prior to the study visit by telephone. Information about the trial is given and the patient brochure is sent to the patient. In this way, patients are already informed about the study at the screening visit and informed consent form can be signed.

The right of a participant to refuse participation without giving reasons must be respected.

The participant must remain free to withdraw at any time from the trial without giving reasons and without prejudicing his/her further treatment and must be provided with a contact point where he/she may obtain further information about the trial. Where a participant is required to re-consent or new information is required to be provided to a participant it is the responsibility of the PI to ensure this is done in a timely manner.

The PI takes responsibility for ensuring that all vulnerable subjects are protected and participate voluntarily in an environment free from coercion or undue influence.

The participant population is not likely to include a significant proportion of participants who cannot read or write, require translators or have cognitive impairment (the patient must be a suited candidate for physiotherapy in order to participate in the trial). However, if present, appropriate alternative methods for supporting the informed consent process should be employed. This may include allowing a witness to sign on a participant's behalf (in the case of problems with reading or writing), designate a legal representative, or providing Participant Information Sheets in other languages or in a format easily understood by the participant population (in the case of minors or cognitive impairment) providing they are approved by the Ethics Committee (EC).

Informed consent will be signed by the patient or a legal representative. In the foot drop trial, the ICF will be discussed and signed at the screening visit. This process will involve:

- discussion between the potential participant or his/her legally acceptable representative and an individual knowledgeable about the research, the nature and objectives of the trial and possible risks associated with their participation
- the presentation of written material (e.g., information leaflet and consent document which must be approved by the EC and be in compliance with GCP, local regulatory requirements and legal requirements)
- the opportunity for potential participants to ask questions
- assessment of capacity. For consent to be ethical and valid in law, participants must be capable of giving consent for themselves. A capable person will:
  - understand the purpose and nature of the research.
  - understand what the research involves, its benefits (or lack of benefits), risks and burdens.
  - understand the alternatives to taking part.
  - be able to retain the information long enough to make an effective decision.
  - be able to make a free choice.
  - be capable of making this particular decision at the time it needs to be made (though their capacity may fluctuate, and they may be capable of making some decisions but not others depending on their complexity).
  - where participants are capable of consenting for themselves but are particularly susceptible to coercion, it is important to explain how their interests will be protected.

General good practice in research (and the basis of legal frameworks) require that persons incapable of giving legal consent should be given special protection.

A person is assumed to have the mental capacity to make a decision unless it is shown to be absent. Mental capacity is considered to be lacking if, in a specific circumstance, a person is unable to make a decision for him or herself because of impairment or a disturbance in the functioning of their mind or brain. In practice for participants with mental incapacity this means that they should not be included in clinical trials if the same results can be obtained using persons capable of giving consent and should only be included where there are grounds for expecting that their taking part will be of direct benefit to that participant, thereby outweighing the risks.

If subjects, who lacks the capacity to consent for themselves, are considered for inclusion, the PI should determine if the patient is incapacitated to participate in a physiotherapy program. If not, the patient is not suited to be included in the trial (inclusion and exclusion criteria).

Where a participant is able to consent for a clinical trial but later becomes incapacitated (for example progressive cancerous disease), in all such cases the original consent given endures the loss of capacity,

providing that the trial has not significantly altered and the patient can continue the physiotherapy program. If cessation of any further clinical intervention or follow-up is mandatory, patients will be analysed according to the intention-to-treat principle (i.e. all patients randomized included in the analyses and analysed in the group to which they were randomized).

### 8.3 Trial randomisation

Trial randomization is mandatory and affords an unbiased comparison between groups as it controls for both known and unknown variables. Through randomization both the conservative and surgical treated group will be balanced regarding prognostic variables. Both treatment groups will be prognostically balanced (with exception of the intervention), so that if a difference in outcome is observed, a sound argument can be made attributing the difference in result to the intervention under study. Simple randomization based solely on a single, constant 1:1 allocation ratio will be used in the foot drop trial.

The Randomization Module within REDCap will be used to assign participants to specific groups (web-based randomisation/treatment allocation system). In this way, an unpredictable allocation sequence will be generated so that the treatment allocation is concealed from the randomizing treating physician. Randomization will be documented by e-mail. Since peroneal nerve entrapment is not a medical emergency, randomization will not be done outside of the office hours. Randomization will not be stratified by centre because of the risk of selection bias due to treatment predictability in centers with low inclusion rates. Furthermore, due to the anticipated low inclusion rate in several centers, an imbalance in the number of patients per study arm can be created when working with stratification by centre. Therefore, randomization will be global over all participating centers. The PI of the local centre, as well as all the treating physicians, and the study coordinator will receive User Rights for the Randomization Module. The study coordinator should have an overview of all the randomizations made in each centre.

### 8.4 Blinding

Blinding of trial participants and care providers is not possible because of obvious differences between both treatment groups: one group will be surgically treated whereas the other group will receive maximal conservative treatment until the primary endpoint is assessed. However, the clinical investigator in the foot drop trial (= outcome assessor) can be blinded to treatment. All participants will be asked to wear long trousers to cover a potential scar at the level of the knee. Furthermore, all patients will be asked to apply a bandage at the site of the operation (or the site of entrapment if there was no operation). Participants are not allowed to discuss their treatment with the outcome assessor. A preassessment contact between the patient and an unblinded member should be organized prior to the study assessments, to remind and instruct patients of the blinding precautionary measures.

Patients in the surgical arm of the trial will be evaluated after 10 days. A postoperative control is considered standard of care. Assessments cannot be performed by the outcome assessor at this stage, as this will cause unblinding.

Since all health care providers have access to the electronic health record, measures should be taken to prevent unblinding of the outcome assessors. Several precautions should be considered:

- Data of assessments will be documented on a separate worksheet, outside the electronic health record so that there will be no need to access the electronic health record.
- If the outcome assessor thinks the electronic health record should be accessed, the treating physician should be consulted. Since the treating physician is not blinded, he/she can access the electronic health record if deemed necessary.

To avoid errors, the outcome assessor must be aware of the identity of the patient during the assessments. Therefore, anonymization during assessment is not possible.

Blinding the outcome assessor will create the opportunity to make an objective assessment of primary and (key) secondary outcome parameters, without increasing the risk of bias.

Until the time of unblinding for final data analysis, the randomization list is kept strictly confidential. The randomization list is accessible only by the REDCap data manager to prevent further selection bias. The statistician should neither have access to randomized treatments (or randomization list) nor even to the full database until the database has been locked for analysis.

## 8.5 Unblinding of outcome assessor

Full randomization information will be made available for data analysis only after database lock. Given the fact that both the care providers and patients aren't blinded, situations that require unblinding of the outcome assessor during the trial will be rare. Surgical complications can occur in the postoperative period, during which the patient is followed by the treating physician. In situations where the patient signals treatment related problems during the examination by the outcome assessor, the treating physician should be consulted. The treating physician, who is not blinded can assess the problems of the patient and can decide if unblinding of the outcome assessor is necessary. Where possible, the outcome assessor should remain blinded.

Accidental unblinding of outcome assessors can happen. Measures will be taken to anticipate the occurrence of such event. A preassessment contact with an unblinded member of the study team will be scheduled prior to the study visit, to remind patients of the blinding and help them with placing the bandage or other blinding material. In all participating centers, at least 2 outcome assessors should be trained and deployable. In case of accidental unblinding of one outcome assessor, the other outcome assessor can follow-up on the particular patient during the remaining study visits.

The study code should only be broken for valid medical or safety reasons e.g. in the case of a severe adverse event where it is necessary for the investigator or treating health care professional to know which treatment the patient is receiving before the participant can be treated. In the foot drop trial, these situations will be virtually non-existent, since the treating physician is not blinded.

The occurrence of any emergency unblinding during the study must be clearly justified and explained by the investigator. In all cases, the sponsor personnel must be informed about the reason for unblinding as soon as possible before or after the event. The circumstances leading to unblinding must be documented in the hospital charts, the Investigator Site File (ISF) and in the eCRF. If unblinding occurs, all assessments as defined in the study protocol must still be performed, unless the subject withdraws consent to participate in the study.

## 8.6 Baseline data

Baseline data can be collected by the treating physician during the **screening visit** and will be recorded in the eCRF.

- EDX characteristics (see also 8.7.2.)
- Sex (male/female)
- Height in centimetres
- Age in years
- Site of entrapment (left/right/bilateral)
- Time since onset of foot drop in weeks
- MRC score for ankle dorsiflexion and ankle eversion at presentation
- Subacute onset (>2days) of foot drop
- Weight loss during last 6 months:

- Weight loss in kg
  - Current weight
  - BMI (kg/m^2)
  - Is weight loss intentional?
  - Weight loss after bariatric surgery?
  - Rapid onset?
- Postural neuropathy
  - Habitual leg crossing?
  - Prolonged squatting?
  - Frequent kneeling?
- Exercise (dynamic compression)
- Onset after childbirth?
- Previous lumbar surgery?
- Trauma
  - Sharp/blunt
  - Inversion trauma of the ankle
  - Knee dislocation
  - Other
- Iatrogenic causes of peroneal neuropathy
  - Surgery of the hip/knee/ankle
  - Other surgery (e.g. wrong positioning during thoracic surgery)
  - Recent bracing/ pneumatic compression device/ compression wrapping
  - Other
- Metabolic/systemic disease
  - Diabetes mellitus
  - Thyroid disease
  - Vitamin deficiencies e.g. B12
  - Oncological history
  - Other
- Prolonged bedrest
- Professional occupation
- Use of alcohol in units/week
- Tinel sign at the level of the fibular head
- History of neuromuscular diseases
- Professional disability
  - Currently employed/working?
  - Ability to continue working? (last day of work if the patient is unable to work)

**Baseline assessment** for the primary and secondary endpoints analyses will be collected at the **randomisation visit** by the **outcome assessor** (blinded researcher), this will reduce inter-observer variability during follow-up. The limited baseline assessments conducted by the treating physician should be conducted before the actual randomization to avoid bias. The EQ5D-5L is only to be registered if the patient did not complete the online survey or if the patient chose to not use the online system.

Baseline primary and secondary endpoint data will include:

- MRC-score for ankle dorsiflexion, hallux extension and ankle eversion
- Gait assessment:
  - o **Distance covered during the six-minute walk test (primary outcome)**
  - o Gait speed during the 10 meter walk test
  - o Ability to walk barefoot
  - o Stanmore questionnaire
  - o Need for foot-ankle-orthosis
  - o Functional ambulation categories
- Sensory changes
- Quality of life questionnaire
  - o EQ-5D 5L
- Work and Productivity Impairment Questionnaire (WPAI)

## 8.7 Trial assessments

In the section below, all study procedures and trial assessments are described, as well as their timing. Several assessments will be performed by the treating physicians, others by the outcome assessor (blinded researcher). The study assessments are listed in the visit and assessment schedule (see Section 8.8).

A list of standard assessments (clinical records, considered daily practice; including motor and sensory function, ability to walk (barefoot), need for orthosis, treatment) will be composed for uniformity across centers. These data will be collected at every study visit and will be recorded in the eCRF. The list of standard assessments is included in appendix 4.

Several questionnaires (EQ-5D 5L, WPAI) will be made available as an online survey (REDCap) for patients. All other questionnaires completed by the subject or proxy are entered into the corresponding eCRF form by the study coordinator. The original paper copies of the questionnaires that are not available online will be filed in the ISF and made available for verification by the site monitor. If patients fail to complete the survey online, the blinded researchers can make sure that the questionnaires are complete during follow-up. If the patient is unable to return to the investigative site for study specific follow-up, the questionnaires will be sent to the patient's home (and the clinical evaluation will be recorded as missing data). Patients will receive a message prior to each evaluation moment, to remind them of the upcoming assessments. At every assessment, the schedule of the assessments to come will be discussed with the patients as an extra reminder.

If visits or data collection time-points are missed, despite previous mentioned efforts, following measures will be taken:

- The outcome assessor will inform the treating physician, PI, clinical trial assistant or any other non-blinded study personnel. The patient will be contacted to reschedule the visit as soon as possible. This cannot be done by the outcome assessor to guarantee blinding.
- If the patient is not able to reschedule, the reason will be documented in the eCRF. If possible, certain assessments will be evaluated through telephone:
  - o EQ-5D 5L questionnaire

- WPAI questionnaire
- Sensory changes
- Ability to walk barefoot
- Need for foot-ankle orthosis
- Return to work
- Registration of treatment
- The scheduling of the following appointments will be checked with the subject, to be sure that further follow-up is guaranteed.

The site and study team must take preventive measures to avoid a subject being lost to follow-up (at least 3 contacts (e.g., telephone calls or e-mails) must be placed to the last available telephone number or e-mail address) and 1 registered letter must be sent by post to the last available home address. If the subject is still unreachable after all contact attempts listed above, he/she will be considered to be lost to follow-up.

If a patient decides to not attend to some follow-up visits (for example a patient with fast recovery after surgery), efforts should be made to convince the patient to agree to the study visit at 9 months after randomization. The visit at 9 months is the most important study visit due to assessment of the primary endpoint. In this way, the patient is not lost to follow-up and the other visits will be marked as 'missed data collection time-points'.

For protocol non-adheres, all endpoints will be assessed according to protocol if the patient chooses to remain included in the trial.

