#### **11.4.4 Secondary outcome analysis**

The key secondary endpoint is the timing of recovery (defined as the time necessary to cover the minimal age- and sex-specific normal distance in meters during the six-minute walk test AND the time necessary for foot drop to recover to a MRC-score  $\geq 4$  for ankle dorsiflexion). However, the study will be only powered for the primary endpoint but if the primary endpoint should show a significant difference, it is anticipated that also the timing of recovery might yield a significant effect. Motor strength will also be assessed at the following time points: at 6 weeks, 3 months, 6 months and 9 months. The time of recovery will be analysed using a generalized log-rank test with constant weights over time for interval-censored data. In addition, the Turnbull estimator with 95% confidence intervals will be produced. The estimated proportion of patients which are recovered will be estimated at 6 weeks, 3 months, 6 months and 9 months. We do not anticipate any mortality due to the pathology. In case a patient should die, the patient will be censored at his day of death.

Full details on the analysis of the key secondary endpoint and the analysis of the other secondary endpoints will be described in the SAP.

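### Section 8.7 accepts visits skipped because of recovery, which the interval-censored analysis of time to recovery does not correct; unequal skipping can bias the comparison against surgery

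*Protocol*

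**What the plan says.** Section 8.7 contains two rules.

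- **Missed visits in general.** "The patient will be contacted to reschedule the visit as soon as possible". "If the patient is not able to reschedule, the reason will be documented in the eCRF". "If possible, certain assessments will be evaluated through telephone"; the list that follows has neither the six-minute walk test nor the MRC score. For a patient who cannot return to the site, questionnaires are posted, "and the clinical evaluation will be recorded as missing data".
- **Patients who choose to stay away.** The rule opens "If a patient decides to not attend to some follow-up visits (for example a patient with fast recovery after surgery". In that case "efforts should be made to convince the patient to agree to the study visit at 9 months after randomization", and "the other visits will be marked as 'missed data collection time-points".

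Sections 4.3.2 and 8.7.1 define recovery by two criteria together: 82% of the predicted walk distance and an MRC score of at least 4 for ankle dorsiflexion. Section 5.1 sets the visits at 6 weeks and 3, 6 and 9 months. The 10-day surgical check in the Section 8.8 table has no walk test, so it cannot date recovery.

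On analysis, Section 11.4.4 says: "The time of recovery will be analysed using a generalized log-rank test with constant weights over time for interval-censored data". It adds the Turnbull estimator and states that the study is powered only for the primary endpoint.

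**The concern.** An interval-censored analysis is valid when the reason for a gap between visits is unrelated to when the event occurred. In the example that Section 8.7 gives, the event causes the gap: the patient is absent because of recovery. If no earlier visit documented that recovery, the patient is next seen at month 9 and contributes an interval of up to 0 to 9 months. The estimator then spreads this patient over the whole interval in the pattern of those who kept attending, so early recovery is understated.

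Section 2 asks whether surgery brings faster as well as better recovery, and Section 8.7.16 expects the largest difference in return to work at six weeks. The lost information lies in that early period. An analysis plan cannot recover a 6-week walk distance and MRC score that nobody measured, so this is a matter of data collection before it is one of analysis.

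**Working it through.** **1. The plan's own figure.** Section 11.1 assumes an effect size of 0.5, 90% power and two-sided 5%. The normal approximation gives 2 × (1.960 + 1.282)² / 0.5² = 84.1, so 85 per arm. The exact t calculation gives 86 per arm (power 0.903), that is 172. With 5% dropout, 172 / 0.95 = 181.05, so 182. Both stated figures reproduce. The simulations use 86 per arm. The protocol states no figure for time to recovery or for skipped visits.

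**2. What the Turnbull estimator does with a skipper.** Let p₁ be the true probability of recovery by 6 weeks, P that by 9 months, and q the share of those recovered by 6 weeks who are next seen at month 9. The estimate must satisfy

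p̂₁ = (1 − q)p₁ + q·p₁·(p̂₁ / P), so p̂₁ = (1 − q)p₁ / (1 − q·p₁/P).

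P is unchanged, because every skipper recovered at month 9 still counts as an event. Take assumed surgical recovery of 45/65/75/80% at 6 weeks and 3, 6 and 9 months:

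- q = 20%: 0.360 / 0.8875 = 0.406 (simulated 0.408)
- q = 30%: 0.315 / 0.83125 = 0.379 (simulated 0.381)
- q = 50%: 0.225 / 0.71875 = 0.313 (simulated 0.313)

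At q = 30% only 0.379 / 0.80 = 47% of the skippers are put back into the first six weeks, where all of them belong. If 30% of patients recovering between 6 weeks and 3 months miss the 6-week visit as well, the estimate is 0.315 / (1 − 0.3 × 0.65 / 0.80) = 0.417.

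**3. Effect on the test, skipping in the surgical arm only.** All recovery curves and skipping rates are assumptions.

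- Curves A: surgery as above, conservative 25/45/60/70%; patients recovered by 3 months may skip (400 trials per scenario).
- B and C: exponential recovery with medians 3 v 4.6 and 2.5 v 4 months. Null: 4 months in both arms. In these three, anyone recovered before the 6-week, 3-month or 6-month visit may skip (1,500 trials per scenario).

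| Share skipping | Power, A | Power, B | Power, C | Null: false finding for conservative care |
|---|---|---|---|---|
| 0 | 68% | 68% | 78% | 2.8% |
| 10% | – | 62% | 71% | 4.2% |
| 20% | 52% | 55% | 64% | 6.3% |
| 30% | 44% | 46% | 55% | 9.2% |
| 50% | 34% | 30% | 35% | 17.4% |

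A repeat on curves A at 30% gave power of about 44 to 52%, against 64 to 66% with full attendance. Under the null at 30%, the surgical estimate at 3 months is 0.32 (true 0.41), while at 9 months it stays at 0.79.

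**4. When the effect shrinks.**

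- *6-week visit attended* (curves A, 600 trials; only patients recovering between 6 weeks and 3 months skip): the 6-week estimate stays at 45%. Power is about 64% at 20% skipping and 60% at 30%, against 65% with none.
- *Only patients recovered before 6 weeks skip* (B, 30%): power is 59% instead of 68%. Under the null the mean Z is −0.25, against −0.55 when later recoverers skip too.
- *Both arms skip 30%*: under the null the mean Z is −0.02, as with no skipping. Power is 67% (B) and 76% (C). Both early curves are still too low, for example 0.16 at 6 weeks under the null against a true 0.21.

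**The case against.** The strongest reply is that the protocol already pursues every visit. Section 8.7 provides a message before each evaluation, a reminder of the schedule at each assessment, and rescheduling contact after any missed visit. A reader might infer that only the 9-month visit is chased; the text does not support that. What stands is narrower. For the patient who decides not to come, the specific rule names only the 9-month visit and accepts the other gaps.

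A reader might also infer that the protocol identifies surgical patients as the likeliest to skip. It does not: fast recovery after surgery is only an example, with no rate and no contrast between arms. Section 14.2 gives mixed signals. One pilot patient who questioned the repeated visits reported no progress, and 97% of interviewees would not be deterred from entering by longer follow-up. In the same section, however, almost all surgical patients had been evaluated only once after surgery, whereas half of the conservative patients had at least two evaluations.

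The 6-week visit coincides with a standard-of-care check for surgical complications (Section 8.7.13), so the visit that dates the earliest surgical recoveries may be well attended. This is a fair limit on the size. It is no guarantee, because that check is done by the treating physician and the walk test by the blinded assessor.

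Finally, Sections 11.4.4 and 11.4.5 leave analysis detail and missing data to the SAP. The absence of a sensitivity analysis from the protocol is therefore not itself a fault.

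**Conclusion.** The point holds in conditional form. Section 8.7 accepts absence that depends on the outcome, and the methods fixed in Section 11.4.4 do not correct for it. Early recovery is underestimated in any arm where patients skip before recovery is first documented. The comparison can be biased against surgery if such skipping is more common there.

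It would go too far to say that the comparison is biased, or that early recoveries are lost. Skippers seen recovered at 9 months remain events. A patient already documented as recovered loses no timing by missing later visits. Equal skipping leaves little or no between-arm bias.

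The size rests wholly on assumed skipping rates and recovery curves. With 20 to 30% skipping confined to the surgical arm, power falls by roughly 13 to 24 percentage points in the tabulated scenarios (68% to 55% in B at 20%; 68% to 44% in A at 30%). With the 6-week visit attended, the loss on curves A is about 1 to 5 points.

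The stakes are limited. The endpoint is not powered, and the primary endpoint and the 9-month recovery proportion are unaffected when the 9-month visit is attended. Bias in this direction could hide a benefit of surgery but not create one. The change is worth making because it is cheap and the missing measurements cannot be recovered later.

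**What to change.** In Section 8.7, keep the effort for the 9-month visit and add to it, identically for both arms:

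- A patient who wishes to skip visits because of recovery, and whose recovery is not yet documented, is asked to attend the next scheduled visit so that walk distance and MRC score are recorded.
- Later visits other than the 9-month visit may be marked as missed only once both criteria are documented.
- The reason for any declined visit is coded in the eCRF. The present text records a reason when a patient cannot reschedule; whether this covers a patient who declines is unclear.

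Optionally, the SAP can add a bounding sensitivity analysis in both arms that closes the recovery interval at the first visit missed for perceived recovery. It should be reported beside the main analysis and not instead of it.

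The cost is an extra request to a reluctant patient, one reason code and, if adopted, one more analysis. That bound would rest on the perception of unblinded patients, which may itself favour surgery, so it shows sensitivity and does not correct the estimate.
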